5.3.1 Exploratory Endpoints

1. Static respiratory system compliance at randomization, day 4 and day 7.
2. Invasive bacterial and fungal infections.
3. Organ dysfunction scores (regular SOFA variables including respiratory, coagulation, liver, cardiovascular, CNS and renal; as well as SpO₂/FiO₂ ratio).
4. The NHLBI-endorsed Acute Respiratory Failure Core Outcome Measurement Set (COMS) in survivors at day 180.
5. Risk factors for CMV reactivation (>0 IU/mL, >1000 IU/mL) in plasma and lung
 - a. Sex, age, race
 - b. Co-morbidity
 - c. APACHE III score at baseline
 - d. SOFA score and individual components
 - e. Lymphocyte count
 - f. Time from hospital admission
 - g. Viral load prior to randomization
6. Relationship of CMV viral load with RSFDs and VFDs and secondary clinical outcomes:
 - a. Viral load: initial, peak, slope, area under the curve (AUC)
 - b. Association with RSFD and VFD, day-28 mortality, duration of mechanical ventilation in survivors, static compliance, and PaO₂/FiO₂.
 - c. Baseline viral load in plasma and lung.

7. Viral load kinetics among survivors in day 7 and 14.
8. Sensitivity, specificity, PPV and NPV of rapid lateral flow CMV serostatus assay.
9. CMV cellular immunity, neutralizing antibodies, antibody epitope expansion, and transcriptional signatures.
10. Use of ECMO at any time during the post-randomization period, and duration if used
11. Occurrence of neuromuscular blockade.
12. Prone positioning status.

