We will also compare the duration of mechanical ventilation and respiratory support by day 28 among survivors between the two intervention arms. If the rate of death by day 28 differs between the two groups, then the analysis in survivors may be biased. If there is evidence for a differential death rate, then a sensitivity analysis will be conducted to evaluate how the estimated mean difference changes with a range of assumptions about the degree of possible selection bias. The sensitivity analysis method of Shepherd will be used [91], which was designed to address “truncation by death”. A mediation analysis will also be conducted to test if CMV viremia lies in the causal pathway linking the treatment (Ganciclovir) effect with the outcome (RSFDs), that is,

if CMV viremia, which is assumed to be affected by the treatment, itself affects the outcome or not.

This analysis will be conducted in four steps:

1. A regression analysis with Treatment predicting RSFDs to test for path c alone,
2. A regression analysis with Treatment predicting CMV Viremia to test for path a,
3. A regression analysis with CMV Viremia predicting RSFDs to test the significance of path b,
4. A multiple regression analysis with Treatment and CMV Viremia predicting RSFDs.

The purpose of Steps 1-3 is to establish that zero-order relationships among the variables exist. If one or more of these relationships are non-significant, it can be concluded that mediation is not likely. If there are significant relationships in Steps 1 through 3, Step 4 is conducted. In the Step 4 model, some form of mediation is supported if the effect of CMV Viremia (path b) remains significant after controlling for Treatment. If Treatment is no longer significant when CMV Viremia is controlled, the finding supports full mediation. If effect of CMV Viremia is still significant, the finding supports partial mediation. Apart from this, static respiratory system compliance (Crs) will also be used in a separate mediation analysis to understand whether any effect of Ganciclovir is exerted via pulmonary mechanisms.

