7.4 Exclusion criteria

1. Known or suspected immunosuppression, including:
 - a. HIV+ (i.e. prior positive test or clinical signs of suspicion of HIV/AIDS; a negative HIV test is not required for enrollment)
 - b. stem cell transplantation:
 - i. within 6 months after autologous transplantation or
 - ii. within 1 year after allogeneic transplantation (regardless of immunosuppression)

- iii. greater than 1 year after allogeneic transplantation if still taking systemic immunosuppression or prophylactic antibiotics (e.g. for chronic graft versus host disease)

Note: if details of stem cell transplantation are unknown, patients who do not take systemic immunosuppression and do not take anti-infective prophylaxis are acceptable for enrollment and randomization.

- c. solid organ transplantation with receipt of systemic immunosuppression (any time)
- d. cytotoxic anti-cancer chemotherapy within the past three months (Note: next-of-kin estimate is acceptable)
- e. congenital immunodeficiency requiring antimicrobial prophylaxis (e.g. TMP-SMX, dapsone, antifungal drugs, intravenous immunoglobulin)
- f. receipt of one or more of the following in the indicated time period (see Appendix C):
 - i. within 6 months: prednisone, alemtuzumab, antithymocyte/antilymphocyte antibodies, or other immunosuppressive drugs associated with CMV reactivation

Note:

- If no information on these agents is available in the history and no direct or indirect evidence exists from the history that any condition exists that requires treatment with these agents (based on the investigator's assessment), the subject may be enrolled. For all drug information, next-of-kin estimates are acceptable. See Appendix C for commonly prescribed immunosuppressive agents. Information on the use of biologics with moderate immunosuppressive effect but no known effect on CMV are permitted and will be recorded in the CRFs.
- An average of >20mg/day of prednisone for the past 30 days prior to hospital admission. The total prednisone intake should be added and averaged over 30 days. For example, a patient taking 40mg/day for 14 days would not be excluded because $(40 \times 14) / 30 = 18.7$. Other steroids should be converted into prednisone equivalents. Additionally, any dose of corticosteroids given for any reason on or after hospital admission is acceptable.

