9.3 Screening procedures

Screening procedures are done to determine eligibility and to provide a baseline for comparison of data. Baseline data are obtained during screening. All inclusion and exclusion criteria must be assessed within 120 hours before randomization. Importantly, the patient can only be randomized once these test results are available.

Before randomization, the following procedures are performed:

- Clinical laboratory tests as defined in the inclusion and exclusion criteria, including:
 - Serum or urine pregnancy test—the results of this must be negative before proceeding, since ganciclovir is suspected to be teratogenic.
 - CMV serology by lateral flow assay (LFA) or gold standard test. See **Figure 9-1 and Section 9.3.1** for the specific algorithm by which the LFA and confirmatory gold standard test will be used for CMV serology.
 - Leftover serum (preferred) or plasma may be used if available.
 - If leftover material is not available, a small amount of extra blood (0.5-1.5 ml) should be obtained after prescreening consent is administered to permit such testing. Prescreening consent may be obtained verbally or as written consent, as permitted per IRB guidelines.
 - After lateral flow testing is obtained, a portion of the same sample should be sent to a CLIA-approved lab for testing.
 - Absolute neutrophil count/total white blood cell counts

- Collection of medical history
- Collection of samples for CMV PCR in plasma and endotracheal aspirates as well as for storage for subsequent CMV immunity testing, genomic analysis, and ancillary studies
- Assessment of select concomitant medications: steroids, immunosuppressive medications and antivirals
- Net fluid balance at ICU admission
- Obtaining of patient demographics in compliance with the NIH Policy on Reporting Race and Ethnicity Data: Subjects in Clinical Research, Aug. 8, 2001. Available at <http://grants.nih.gov/grants/guide/notice-files/NOT-OD-01-053.html>

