9.6 First dose of study drug

Study day 1 is defined as the first calendar day on which the patient is randomized and the first dose of study drug is administered. All subsequent study days will start accordingly. At baseline, but before administration of study drug, the following procedures will need to be performed:

- Blood: Creatinine, CMV cell-mediated immunity, platelets, CMV plasma PCR, CBC w/differential, research samples.
- Endotracheal aspirate (ETA). If patient is intubated, collect an ETA specimen at baseline (\pm 1 day) and twice weekly, at the time that this procedure is routinely performed by respiratory therapy. Specimens will be labeled and stored frozen for subsequent CMV PCR analysis at the coordinating lab at Fred Hutch.
- Clinical Assessments: Apache III, SOFA, COMS survey (see Section 9.10), static respiratory compliance, ventilator parameters, assessment of select concomitant medications (steroids, immunosuppressive medications, neuromuscular blockers, and antivirals), use of ECMO and prone positioning, and bilateral vs. unilateral infiltrates on chest radiograph. See Section 9.11 for details on these assessments.

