9.11 Post-Enrollment Procedures

See the schedule of procedures for specific time points (including permissible windows) in Appendix A. Duration of participation in the study by individual patients will be 180 days.

- Blood:
 - Creatinine, Platelets, CBC w/differential - Days 4, 7, 11, 14, 18, 21, 25, 28 (all \pm 1 day); can be obtained from clinical testing results if available
 - CMV PCR (all \pm 1 day):
 - At intensified monitoring sites: Days 4, 7, 11, 14, 18, 21, 25, 28
 - At all sites: 7, 14, 21, 28 at all sites
- ETA: At intensified monitoring sites, CMV PCR, twice weekly (\pm 2 days) while intubated.
- Clinical Assessments:
 - SOFA score daily on Days 1-7, then twice weekly (Day 11, 14, 18, 21, 25, 28) through day 28 if still in the ICU
 - Vital status (collected as ICU and hospital mortality at discharge, and 180-day mortality)
 - Assessment of concomitant antiviral medications daily on Days 1-7, then twice weekly through day 28
 - Ventilator parameters and static respiratory compliance (daily if mechanically ventilated), NIV parameters, and HFNC parameters daily.
 - Net fluid balance at ICU admission and net cumulative fluid balance until ICU discharge
 - Use at any point during study (and if used, duration/number/dose) of ECMO, prone positioning, steroids, neuromuscular blockers; collected at hospital discharge
 - Occurrence of bacteremia and fungemia; collected at discharge
 - Use of antibacterials or antifungals in the event of ventilator-associated pneumonia or nosocomial pneumonia (defined as sputum, BAL or ETA culture with new pathogen associated with new antibiotic +/-48 hours from culture). Any antibacterial used to treat bacteremia or antifungal used to treat fungemia should be reported.
 - Apache III at baseline only
 - COMS survey (see Section 9.10) at Day 180 (\pm 6 weeks)
 - Bilateral versus unilateral infiltrates on chest radiograph: To be assessed as close as possible to, but not prior to, randomization. Chest radiograph at admission is acceptable if it is the only one available. If the word "bilateral" is not on the report of the chest radiograph, then the coordinator will ask the site PI to assign unilateral, bilateral, or "no infiltrates" to the patient's chest radiograph. If the word bilateral is in the report, then the coordinator will assign bilateral.
- For women of childbearing potential, a serum pregnancy test will be performed at day 7 or at the time of hospital discharge if discharged before study day 7.

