APPENDIX C: COMMONLY PRESCRIBED IMMUNOSUPPRESSIVE AGENTS WITH KNOWN EFFECT ON CMV REACTIVATION

Generic Name	Trade Name
Antithymocyte Globulin (Equine)	ATG, ATGAM
Antithymocyte Globulin (Rabbit)	Thymoglobulin
Alemtuzumab	Campath
Prednisone ^a	

^a An average of >20mg/day of prednisone for the past 30 days prior to hospital admission. The total prednisone intake should be added and averaged over 30 days. For example, a patient taking 40mg/day for 14 days would not be excluded because $(40 \times 14) / 30 = 18.7$. Other steroids should be converted into prednisone equivalents. Additionally, any dose of corticosteroids given for any reason on or after hospital admission is acceptable.

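### The mediation regressions for the CMV-to-RSFD path carry no baseline severity or steroid covariates, so that path is open to confounding of unknown size and sign

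*Combined protocol and SAP*

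**What the plan says.** Protocol Section 6.2.2 sets out four regressions:

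1. treatment on RSFDs (path c);
2. treatment on viremia (path a);
3. viremia on RSFDs (path b);
4. "A multiple regression analysis with Treatment and CMV Viremia predicting RSFDs".

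Step 4 runs only if Steps 1 to 3 are all significant. A viremia term that stays significant in Step 4 is then taken as support for mediation. It is called full mediation if the treatment term loses significance. The only covariates that could reach these models from elsewhere are gender and race/ethnicity, which Section 6.2.1 says will be included and examined in primary, secondary and exploratory analyses. The SAP does not describe the mediation analysis.

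On steroids, Section 7.4 excludes "An average of >20mg/day of prednisone for the past 30 days prior to hospital admission" but adds that "any dose of corticosteroids given for any reason on or after hospital admission is acceptable". Appendix C, titled "COMMONLY PRESCRIBED IMMUNOSUPPRESSIVE AGENTS WITH KNOWN EFFECT ON CMV REACTIVATION", lists prednisone with a footnote repeating both rules. Use is recorded at screening (Section 9.3: "Assessment of select concomitant medications: steroids, immunosuppressive medications and antivirals"), before the first dose (Section 9.6: "assessment of select concomitant medications (steroids, immunosuppressive medications, neuromuscular blockers, and antivirals") and over the stay (Section 9.11: "Use at any point during study (and if used, duration/number/dose) of ECMO, prone positioning, steroids, neuromuscular blockers; collected at hospital discharge").

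Section 5.3.1 item 5, "Risk factors for CMV reactivation (>0 IU/mL, >1000 IU/mL) in plasma and lung", lists demographics, co-morbidity, APACHE III, SOFA, lymphocytes, time from admission and prior viral load. The viral-load and outcome models in Section 6.2.3 name no adjustment covariates.

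**The concern.** The analysis puts a causal question to a variable that was not randomized. Randomization protects the effect of treatment on viremia and on RSFDs. It does not protect the comparison of viremic with non-viremic patients. A baseline factor that influences both viremia and RSFDs produces a viremia coefficient without any effect of the virus, or hides a real one. Under the stated reading rule, the first error appears as evidence of mediation and the second as evidence against it.

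Severity of illness is the obvious candidate. Corticosteroids are a possible one: Appendix C supplies a reason to think they bear on reactivation, and exposure will vary because any in-hospital dose is accepted. At stake is the mechanistic reading of the trial, not its primary result. The clinical rule on steroids is not in question here.

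**Working it through.** **Which paths are exposed**

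| Step | Predictors stated | Protected by randomization? |
|---|---|---|
| 1 (path c) | treatment | yes |
| 2 (path a) | treatment | yes |
| 3 (path b) | viremia | no |
| 4 | treatment, viremia | viremia term: no |

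**Could another section supply the covariates?** Section 6.2.2 also plans adjusted models for RSFDs and other secondary endpoints, but as a separate analysis. Their covariate source is item (1) of Section 5.3, which is static compliance. Section 6.2.3 takes its risk factors from a Section 1 C.2 that this protocol does not contain. SAP Section 5 points to Section 5.3 generally, where steroids are not named. SAP Section 11 sends further analyses to a companion SAP that is not among the documents. The topics it lists do not mention mediation.

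**Design figure reused.** The illustration takes its SD of 9.4 days from protocol Section 6.1.1. That section's sample size reproduces: n = 2(1.960 + 1.036)² × (9.4/2.74)² = 2 × 8.98 × 11.77 = 211.4, so 212 per arm by the normal formula. The exact t calculation gives 213, as stated. Nothing in this point challenges that figure.

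**How large could the bias be?** Inputs:
- From the documents: N = 500, 1:1 allocation, SD 9.4, and viremia of 30% on placebo (Section 2.4.1 gives at least 30%).
- Assumed, not in the documents: viremia 10% on ganciclovir; 30% to 50% of patients on steroids at baseline; steroid–viremia odds ratio 1.5 to 3; steroid–RSFD difference of 2 or 4 days in either direction; no true viremia effect.

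Formula: path-b bias ≈ (steroid–RSFD difference) × (steroid prevalence in viremic minus non-viremic patients, within arm).

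Worked case, 50% on steroids and odds ratio 2:
- Placebo: viremia is 22.8% without and 37.2% with steroids (average 30%). Steroid prevalence is 0.5 × 0.372/0.30 = 0.62 in viremic and 0.5 × 0.628/0.70 = 0.45 in non-viremic patients, a difference of 0.17.
- Ganciclovir: the same steps at 10% viremia also give 0.17.
- Bias: 0.17 × 4 = 0.68 days. Simulation of Step 4 by least squares (2,000 runs) gave 0.67.

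Over the whole grid:

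| Step 4 model | Mean path-b estimate (truth 0) | Rejection at 5% |
|---|---|---|
| treatment + viremia | 0.15 to 1.04 days in absolute value, sign following the assumed steroid–RSFD sign | 5.2% to 16.8% |
| + baseline steroid use | within 0.06 days of 0 | 4.4% to 5.8% |

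Cross-check of the top end: the standard error of path b is about 9.4/√(250 × 0.21 + 250 × 0.09) = 9.4/√75 = 1.09 days. A shift of 1.04 days is 0.96 standard errors, and a two-sided 5% test then rejects about 16% of the time, in line with the simulation.

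The illustration uses normal errors, whereas Section 4.5.1 expects RSFDs to be bimodal. It covers steroids only. The same formula applies to any severity measure, but the documents give no inputs for one.

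**The case against.** **Confounding is not demonstrated.** This stands. A reader might infer that the omission does confound the CMV–RSFD link. The documents report no steroid–RSFD relation, and Appendix C ties prednisone to exposure in the 30 days before admission. They do not say that in-hospital courses raise reactivation. On severity, Section 2.4.1 reports no independent association with reactivation, and Section 2.5.4 reports an inconsistent and small one for APACHE. What remains is that the path is unprotected, and that Section 5.3.1 still treats APACHE III, SOFA and prior viral load as candidate risk factors.

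**The analysis is gated.** This largely stands. Step 4 needs significant Steps 1 and 2, both randomized comparisons, so a spurious viremia association alone cannot be declared mediation. SAP Section 4 records closure of enrollment over safety and futility concerns, which makes a significant benefit at Step 1 less likely. The gate does not repair Step 4 once reached, and Step 3, itself part of the gate, is exposed.

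**Steps 1 to 3 are meant to be unadjusted.** Fair. The unadjusted Step 3 can stay, with an adjusted version beside it.

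**The size could be misread.** A reader might set the 0.15 to 1.0 day against the 2.74-day design difference or the 1.5-day minimal important difference in Section 4.5.1. Those are yardsticks for treatment effects; this is a contrast between viremic and non-viremic patients. Carried into a mediated treatment effect under the assumed 20-point viremia reduction, it is 0.20 × 0.15 to 0.20 × 1.04, or about 0.03 to 0.21 days. The plan judges mediation by significance, so the distorted path-b test is the relevant consequence.

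**Steroids are missing from the risk-factor lists.** This adds little. The Section 5.3 objective is worded as an open list, and leaving steroids out of a model for reactivation does not confound the link from CMV to RSFDs.

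**The team's pooled analysis is no precedent for steroids.** Correct. Figure 2-3 in Section 2.4.2 adjusted for age, race, gender, transfusion, cohort and an APACHE score. It is a precedent for severity adjustment, which Step 4 lacks.

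**Conclusion.** The point holds for the viremia-to-RSFD path only. As written, Step 4 and the Step 3 gate are open to confounding by baseline severity, and possibly by in-hospital steroids, with at most gender and race/ethnicity adjusted for. The documents fix neither the size nor the sign of any bias. The range of about 0.15 to 1.0 day, with rejection up to 17% at a nominal 5%, rests entirely on the assumed steroid prevalence, odds ratio, steroid–RSFD difference and viremia reduction. At the weak end of those assumptions the effect on the test is negligible. The treatment-to-viremia and treatment-to-RSFD comparisons and the primary t-test are not affected. The companion exploratory SAP was not available, so it could already contain an adjusted mediation model. This is a worthwhile, low-cost correction to a gated secondary analysis.

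**What to change.** - Prespecify Step 4 with baseline APACHE III, SOFA, age, mode of respiratory support, baseline CMV viral load and pre-dose systemic steroid use (yes/no) as covariates. Report an adjusted Step 3 beside the unadjusted one.
- Baseline viral load matters in its own right: Section 6.1.1 expects about 12% of participants to be PCR positive at baseline, so some viremia predates treatment.
- Use the same covariates in the viral-load and outcome models of Section 6.2.3.
- Do not enter on-study steroid use as if it were a baseline covariate. It is recorded after randomization and may itself be affected by treatment.
- State that the mediation result assumes no unmeasured confounding between viremia and RSFDs.
- Adding steroids to the risk-factor list in Section 5.3.1 is optional.

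The cost is a short text change and a few degrees of freedom in a gated secondary analysis. The plan already collects these variables at screening or baseline, and the primary analysis does not change.

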2.5 Sample Size and Power

To estimate the required sample size for this study, we used ventilator-free days (VFD) data from the GRAIL Phase 2 trial and available literature on RSFDs, assuming similar variance. A clinically meaningful difference in RSFDs between treatment arms was assumed to be 2.74 days, with an empirically estimated standard deviation of 9.4 days. To detect this difference with 85% power using a two-sided test at a 5% significance level, a total sample size of 426 participants (213 per group) was required for the primary analysis.

To account for feasibility and potential dropout—including 1% lost to follow-up and 2% early discontinuation due to negative CMV ELISA results—the final sample size was increased to 500 participants. A pre-specified sample size re-estimation was conducted after 50% of participants had reached the primary endpoint; based on the observed data, the original sample size was retained.

Mortality was included as a secondary endpoint. Assuming a 20% mortality rate in the control arm, the final sample size of 500 provides 80% power to detect a hazard ratio of 0.52 between the Ganciclovir and placebo groups.

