First, biologically, we believe that CMV prophylaxis is likely to exert its greatest effect on pulmonary related morbidity. Second, VFDs (and more recently, RSFDs or organ support-free days) are frequently used as outcomes in high profile RCTs and influence clinical practice. A recent review of 128 RCTs assessing duration of mechanical ventilation in 10 high-profile general medical and critical care journals found that 43% reported VFDs and 12% used it as the primary outcome variable [81]. The NHLBI ARDS Network FACTT Trial showed that a conservative approach to fluid management increased VFDs by 2.5 with no statistically significant effect on mortality at 60 days [82]. Based primarily on this trial evidence, the Surviving Sepsis Guidelines endorsed this approach with a strong recommendation. Finally, VFDs are the outcome that was significantly improved in our phase 2 GRAIL RCT. Importantly, in recent trials enrolling NIV patients, there has been a change from VFDs to RSFDs and organ support free days in a 28 day window [83–85]. For example, the REMAP-CAP platform trials for COVID and community acquired pneumonia have adopted RSFDs and have determined that 1.5 RSFDs are the minimal clinically important difference [84].

There are several possible limitations to using RSFDs at 28 days as our primary endpoint. As with all composites, patients and clinicians may not value these outcomes in the way they are weighted in the composite. RSFDs will not capture outcomes that go in different directions (e.g., treatments that increase mortality but also reduce duration of respiratory support in survivors). RSFDs can be difficult to interpret as they do not simply reflect either a change in mortality or a difference in duration of respiratory support. Generally, VFDs have a bi-modal distribution and must be analyzed appropriately [81]; we anticipate that the distribution of RSFDs will also have a bi-modal distribution.

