In the GRAIL Phase 2 trial, VFDs difference was estimated to be 2.74 days. As shown in Table 6-2, to detect a similar difference (of 2.74 days) in RSFDs between the two arms with 85% statistical power, a sample size of 426 subjects ($213 \times 2 = 426$) total is required in this Phase 3 trial's primary analysis, and that is what we power for in this study. Findings from previous RCTs suggest that approximately 12% of subjects in this Phase 3 RCT will be CMV PCR positive at baseline when rapid lateral flow assay is used to assess serostatus. This 12% estimate is lower than the proportion reported in the GRAIL Phase 2 study due to the use of the rapid lateral flow assay, which we estimate will shorten the time to randomization from ICU admission by approximately 1 day and reduce the baseline PCR positivity rate. Furthermore, we anticipate that the percentage of subjects who are PCR positive at baseline will be lower among individuals on respiratory support (as defined in Section 4.1.1) compared with individuals on mechanical ventilation alone (as in the GRAIL Phase 2 trial) because we will be capturing some eligible participants earlier in the course of their respiratory failure when less time has elapsed to allow for CMV reactivation (both because we will allow enrollment of patients on NIV and HFNC oxygen and because time to obtain consent from participants able to consent for themselves may be shorter than consent through LARs. Since the population for primary analysis includes all patients without regard to PCR positivity at baseline, we inflate the sample size by a factor to

account for the power loss by including these cases in our primary analysis population. We also assume a dropout rate of 1% lost to follow-up for the primary endpoint, based on findings from other large ICU trials, and a dropout rate of 2% for early discontinuation following a negative CLIA CMV ELISA test among randomized participants who have received at least one dose of study drug. Accounting for both of these effects, the sample size for GRAIL Phase 3 trial was increased to 500 subjects in total.

6.1.2 Power Calculations for Secondary Endpoints.

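### The mediation rule reads a non-significant direct effect as full mediation, in a trial with low power to see a direct effect

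*Combined protocol and SAP*

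**What the plan says.** The mediation plan is in Section 6.2.2 of the combined protocol. It runs four regressions: treatment on RSFDs, treatment on CMV viremia, viremia on RSFDs, and then treatment and viremia together on RSFDs. Step 4 is run only if Steps 1 to 3 are all significant. Some mediation is supported if viremia stays significant in Step 4. The full-mediation rule follows: "If Treatment is no longer significant when CMV Viremia is controlled, the finding supports full mediation". The partial-mediation sentence after it depends on viremia, not treatment, still being significant.

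The same section adds that "static respiratory system compliance (Crs) will also be used in a separate mediation analysis", without giving that analysis a decision rule of its own.

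The section asks for no estimate or interval for the direct or indirect effect, sets no bound for a negligible direct effect, and gives no power for Step 4. The standalone SAP does not describe the mediation analysis, and its Section 12 (changes from protocol) does not say it was dropped.

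The only sizing is for the total effect. SAP Section 2.5 says "a total sample size of 426 participants (213 per group) was required for the primary analysis".

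**The concern.** Full mediation means that the effect of treatment not passing through the mediator is zero. A p-value above 0.05 for that effect does not show this. It says only that the data cannot separate the effect from zero, which is the expected result when the estimate is imprecise.

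Part of the total effect is smaller than the whole. Estimating it in a model that also contains a correlate of treatment costs further precision. A trial sized for the whole will therefore often fail to detect a substantial part, and the rule turns that failure into a statement about mechanism.

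At stake is how a positive trial would be explained. The primary hypothesis is benefit through CMV suppression, and the full-mediation label would say that measured viremia accounts for all of it.

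**Working it through.** **Inputs from the documents**
- Total effect 2.74 days: "In the GRAIL Phase 2 trial, VFDs difference was estimated to be 2.74 days" (combined protocol, Section 6.1.1).
- SD: "with an empirically estimated standard deviation of 9.4 days" (SAP Section 2.5).
- Test: "using a two-sided test at a 5% significance level"; sizing: "To detect this difference with 85% power" (both SAP Section 2.5).
- 500 participants, 1:1, so 250 per arm.
- Untreated patients: Section 2.4.1 of the combined protocol puts viremia at 30% or more, and overall reactivation including the lung at about 40%.

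**Assumptions**
- Viremia on ganciclovir. The text says reactivation was suppressed but gives no rate. I use 10-12%, with 5-20% as the wider range.
- Half of the total effect, 2.74/2 = 1.37 days, does not pass through measured viremia. The documents give no direct effect.
- Binary viremia, normal errors, no mediator-outcome confounding.

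**Step 1: reproduce the plan's figure.** n = 2[(1.960 + 1.036) x 9.4/2.74]^2 = 211.3, or 212 per arm by the normal approximation. The t-based calculation gives 213, as stated. Power for 2.74 days is 85% at 213 per arm and 90% at 250.

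**Step 2: precision of the direct effect.** SE = SD x sqrt(2/n) / sqrt(1 - r^2), where r is the treatment-viremia correlation: r = [(p0 - p1)/2] / sqrt[p(1 - p)], with p the mean of the two rates.
- 40% v 12%: p = 0.26, r = 0.14/0.4386 = 0.319. SE = 9.4 x sqrt(2/250)/sqrt(1 - 0.102) = 0.841/0.948 = 0.887. Half-width = 1.96 x 0.887 = 1.74 days.
- 30% v 10%: p = 0.20, r = 0.10/0.40 = 0.25. SE = 0.841/0.968 = 0.868. Half-width = 1.70 days.

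Taking 9.4 as the total rather than the residual SD, and ganciclovir rates of 5-20%, the half-width runs from 1.6 to 1.8 days.

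**Step 3: power for 1.37 days at 250 per arm.** At 40% v 12%, 1.37/0.887 = 1.54, and 1.54 - 1.96 = -0.42, so power is about 34%. Across the assumed rates it is 32-39%. For 85% power, n = 2[(2.996 x 9.4)/1.37]^2 = 846 per arm ignoring the correlation, and about 790 to 1,000 per arm allowing for it.

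**Step 4: simulate the rule.** Trials were generated with 1.37 days direct and 1.37 days through viremia, and all four steps were applied at 0.05. A trial qualifies if Steps 1-3 are significant and viremia is significant in Step 4.

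| Scenario (250 per arm) | Labelled full mediation, among qualifying trials |
|---|---|
| Half direct, viremia 40% v 10-12% or 35% v 10% | 61-63% |
| Half direct, 30% v 10% | 59% |
| One quarter direct | 86-87% |
| Three quarters direct | 30-37% |
| Half direct, true total effect 3.5 days | 47-49% |

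As a share of all simulated trials, the half-direct case gives 54-56% in the first row's scenarios, and 52-56% when 30% v 10% is included. Step 3 implies that treatment is non-significant in about 1 - 0.34 = 66% of all trials at 40% v 12%. Requiring a significant total effect in Step 1 selects trials with larger estimates, which brings the conditional figure slightly lower. A continuous mediator gave 56-72% of trials reaching Step 4.

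**The case against.** Several objections stand and limit the point.

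- **Viremia is not all CMV activity.** A reader might infer that a drug with half its effect outside CMV would be reported as working wholly through CMV. The documents do not support that. The mediator is viremia, and Sections 2.4.1 and 4.2 of the combined protocol say that CMV reactivates preferentially in the lung, can do so without reactivation in blood, and is not always detected by PCR in blood. An effect through lung CMV falls in the treatment term. That term is the effect not through measured viremia.
- **The label is gated.** A reader might infer that the rule confirms the trial's hypothesis by default. It does not: Steps 1-3 and the viremia term must all be significant first, and either label supports some mediation.
- **The majority is modest.** It depends on the share that is direct and on the total effect, and it is lost at about 3.5 days.
- **The text does not settle which label is reported.** Every qualifying trial with treatment non-significant also meets the partial-mediation sentence as worded. The plan also says that the finding supports full mediation, which is softer than concluding it.
- **Practical reach may be small.** SAP Section 4 records that enrollment closed over safety and futility concerns. If Step 1 is not significant, Step 4 is not run.

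None of this rescues the inference. Repairing the partial-mediation wording would leave the full-mediation rule in place, and fewer participants would make the direct effect less precise.

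**Conclusion.** The point holds as a fault in a secondary, gated mechanistic analysis. The rule takes failure to detect a direct effect as support for its absence, where power for a 1.37-day direct effect is about 32-39% and the CI half-width is about 1.7 days. With half the effect bypassing measured viremia, about 61-63% of qualifying trials (59% at 30% v 10%) would receive the full-mediation label.

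The figures rest on 250 per arm, SD 9.4, a total effect of 2.74 days, an assumed ganciclovir-arm viremia rate and no mediator-outcome confounding. Viremia arises after randomisation, so confounding could move the direct-effect estimate either way. The primary RSFD comparison is unaffected.

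A reader might also look for a margin in Section 4.5.1 of the combined protocol, which says that the cited platform trials "have determined that 1.5 RSFDs are the minimal clinically important difference". That figure is a minimal important difference for RSFDs, not a bound for a negligible direct effect. It is 1.5/2.74 = 55% of the design effect, and it would admit the 1.37-day case examined here.

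**What to change.** In Section 6.2.2 of the combined protocol, and in the SAP if the analysis is kept:

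- Delete the full-mediation rule based on treatment losing significance, and the partial-mediation sentence that overlaps it.
- Report the direct effect, named as the effect not through measured viremia, and the indirect effect, each with a 95% CI (bootstrap, for example). The proportion mediated with its CI is optional.
- State that a non-significant direct effect does not show full mediation, and that 500 participants give about 32-39% power for a 1.37-day direct effect under the stated assumptions.
- Do not introduce a margin of 1.5 days either side of zero.
- Report the compliance mediation in the same way.
- Record in SAP Section 12 whether the mediation analysis is retained.

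The cost is wording and a bootstrap, with no new data. The downside is giving up the full and partial labels.
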